Illicit substance use in the United States is a growing concern across all states. Use of illicit drugs such as cocaine, heroin, methamphetamine, prescription opioids and stimulants, and 3,4-methylenedioxymethamphetamine (Ecstasy, MDMA) among others, has remained steady in many parts of the United States¹. Of the 1.2 million PWH in the US, an estimated 48% struggles with a substance use disorder². Poor antiretroviral treatment (ART) adherence and inconsistencies in retention in HIV care has been reported among PWH that use illicit drugs³⁻⁵. Gaps in ART coverage and lack of retention to HIV care are factors that complicate successfully managing PWH who use illicit drugs, often leading to poor treatment outcomes and increased HIV transmission⁶⁻⁸.

The BASE study is a single-arm, pilot study assessing the efficacy and safety of bictegravir/emtricitabine/tenofovir alafenamide, B/F/TAF) over a total of 48 weeks (NCT03998176). At present, roughly 40% of the allotted 45 patients have given consent for BASE study participation with the initial participant's now reaching week 24. Historically, approximately half of the currently enrolled BASE participants have remained out of HIV care and struggled with adherence and ongoing substance use. The study team have been surprised to observe that many of these participants are more engaged in care and not missing study visits. Further, the same participants have reportedly remained adherent to antiretroviral therapy for the first time in years, and some have reduced or ceased their substance use since study enrollment.

In order to examine the underlying reasons for this behavior change, we propose a qualitative study in the form of in-depth, face-to-face interviews with BASE study participants to evaluate the impact of BASE study participation on their treatment adherence, motivations for engagement in HIV care, on-going substance use, mental health, stigma, and access to the necessary support systems.

Hypothesis:

BASE study participation positively impacted the participant's treatment adherence, motivations for engagement in care for HIV, substance use disorders, and mental health.

Objectives:

1. Primary: Determine BASE participant perspectives on how study participation impacted their engagement in HIV care and treatment adherence.
2. Secondary: Determine BASE participant perspectives on how study participation impacted their on-going substance use, mental health, and access to necessary support systems.

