Study Design:**Overview**

This study will be a prospective qualitative study design with interest in examining patient perspectives on the impact of BASE study participation on the following topical domains: treatment adherence, motivations for engagement in HIV care, on-going substance use, mental health, stigma, and access to the necessary support systems. We plan to use a semi-structured, in-depth face-to-face interview to evaluate the topical domains previously listed among participants enrolled in the Phase IV trial in the United States (Effectiveness and safety of Bictegravir/emtricitabine/tenofovir alafenamide (B/F/TAF) in HIV-1 infected patients with Active illicit Substance use [BASE]; NCT 03998176). The anticipated timeframe for in-depth interviews is near the BASE week 48 visit window (42 to 60 weeks).

Sample Size/Justification

A sample size of 10 to 15 participants is typically understood to be a sufficient amount to develop themes within a given group. However, we aim to sample roughly half of the BASE participants (20-25) or until thematic saturation is achieved.

Participants:**Inclusion Criteria**

This study will include participants currently enrolled in the BASE study at the Specialty Care Center in Omaha, NE. We will attempt to balance the enrollment by gender and sociodemographic diversity. A summary of BASE inclusion criteria is below:

9. Inclusion Criteria
 - a. Current participant in the BASE study
 - b. Willing and able to give written informed consent (not severely experiencing psychiatric condition or severely under the influence of illicit substances compromising ability to understand and provide consent)
 - c. English speaking

Exclusion Criteria

1. None

Study Procedures**Recruitment**

Research providers (primary investigator or study team provider) who have already had contact with the participants through the BASE study conduct will identify and directly contact potential study participants during a BASE study visit. If the participant is interested in participating in the qualitative

sub-study, study description and obtaining consent would take place in-person at the Specialty Care Center with a subsequent qualitative study visit scheduled in the future.

All study interactions with potential or enrolled participants will be conducted in a private room at the Specialty Care Center.

Consent Process

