Written informed consent will be obtained for all participants wishing to enroll in the qualitative sub-study. Written informed consenting will be conducted by research providers (primary investigator or study team provider) prior to any interviewing procedures. All consenting will take place at the Specialty Care Center in a private room. All consenting study team members are CITI trained and the consenting study team member will sign off on the consent.

Study Implementation

After consent has been given, each sub-study participant will be interviewed using a semi-structured, in-depth interview guide. The interview guide (Appendix A) contains a listing of open-ended questions with subsequent sub-question probes to elicit participant experiences and perspectives regarding each core topic.

Topics to be explored within the in-depth interviews include:

1. Living with HIV
2. Living with a substance use disorder
3. Engagement in HIV care
4. Views and experiences with study participation

All in-depth interviews will be conducted by a trained interviewer in qualitative research. Interviews will be conducted in English. All interviews will be audio-recorded and transcribed by study team members for data analysis.

Only one in-depth interview will be conducted for each participant. We expect the interviews to be 1 to 2 hours in length. All interviews will take place in a private room. Since participants are enrolled in the BASE study in a rolling fashion, each participant may hit the week 48 study visit window at different time points. Thus, we expect the timeframe for qualitative interviews to take up to 6 months to allow for at least half of BASE participants reaching week 48.

Interview transcripts will be coded through a qualitative software, QSR NVivo. Within each topic of interest, a thematic analysis approach will be utilized toward the coded transcripts. The study team will examine the emerging themes from the data analysis.

All study data including participant contact information will be collected and stored on University of Nebraska Medical Center (UNMC), secure-servers with password-protected files. All interview forms, audio-records, and transcripts will be identified only by the participants BASE patient identification number.

Data Management and Security

Version 5; Last Update 9/22/22

Data Storage

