Appendix A

Interview Question Guide: BASE Participants

PID: _____ Date: _____

Introduction:

Thank you for the opportunity to speak with me today. Please note that this conversation is confidential. We are interested in hearing your opinions and experiences regarding how your participation in the BASE study impacted your motivations for engaging in medical care, your substance use, your mental health and your overall quality of life. May I start by asking you about your experience living with HIV...

Living with HIV

1. What has your experience been like living with HIV?
 - a. Probe: When were you first diagnosed?
 - b. Probe: What experiences did you have coping with your HIV diagnosis?
2. What support systems did you initially have or currently have for coping with your HIV diagnosis?
 - a. Probe: friends, family, partner, support groups, etc
3. What were you initially told about HIV treatment?
 - a. Probe: What feelings did you have regarding the need for life-long treatment?
 - b. Probe: What feelings did you have knowing there was no cure for HIV infection?
4. What experiences have you had with stigma or discrimination because you are living with HIV?
 - a. Probe: Friends, family, partner, work
5. What is the hardest part of living with HIV?
 - a. Probe: Taking life-long medicine, coming to medical visits, dealing with stigma, worry of health, cost of care, etc.

Living with a substance use disorder

1. What has your experience been like living with a substance use disorder?
 - a. Probe: When did you first use an illicit drug and how has your substance use impacted your well-being?
 - b. Probe: What experiences did you have coping with your substance use?
2. What support systems did you initially or currently have for coping with your substance use disorder?
 - a. Probe: friends, family, partner, support groups, etc
3. In what ways has your substance use disorder affected your life?

- a. Probe: Medically, relationships, financial, etc.
4. What experiences have you had with stigma or discrimination because you have a substance use disorder?
 - a. Probe: Friends, family, partner, work
5. What are your experiences with receiving help for your substance use disorder?
 - a. Probe: Describe your experiences with trying to stop or reduce your substance use.
 - b. Probe: How many times have you tried to stop or reduce your substance use?
 - c. Probe: What have been the challenges with stopping or reducing your substance use?

Engagement in HIV care

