1. What does being engaged in HIV care mean to you?
 - a. Probe: Would you describe your engagement in HIV care prior as good or bad? Why?
2. Tell us your experiences with coming to clinic appointments.
 - a. Probe: What barriers have kept you from coming to your appointments?
3. What are your views on what has kept you from coming to your clinic appointments?
 - a. Probe: Medication non-adherence, substance use, homelessness, etc
4. What interventions have helped you to come to your clinic appointments?
 - a. Probe: acute sickness, concern for your health, transportation assistance, gift cards, etc.
5. What experiences have you had with stigma or discrimination when coming to an HIV clinic appointment?
 - a. Probe: What are your feelings about the impact of HIV control (U=U) on stigma related to HIV infection or substance use disorders?
 - b. Probe: What have been your experiences during interactions with medical service providers?
 - c. Probe: Would you describe your experiences with various types of healthcare providers (medical [both HIV providers and non-HIV providers], mental health, etc) as different? Why?

Views and experiences with study participation

1. How did you hear about the BASE study?
 - a. Probe: What motivated you to enroll?
 - b. Probe: What interested you most about the study?
2. What concerns did you have about participating in the BASE study?
 - a. Probe: Privacy, stigma, legal concerns
3. Tell us about your experiences with BASE study participation.
 - a. Probe: Would you describe your experience as positive or negative? Why?

4. How has participating in the BASE study impacted your ability to come to your clinic appointments?
 - a. Probe: What are your feelings of your medical care during participation of the BASE study?
 - b. Probe: What factors have increased or decreased your ability to come to your clinic appointments during the course of the BASE study?
5. How has participating in the BASE study impacted your ability to take your medicine?
 - a. Probe: What factors have increased or decreased your ability to adhere to prescribed medications during the course of the BASE study?
6. What experiences have you had with stigma or discrimination because you participated in the BASE study?
 - a. Probe: Medical providers, friends, family, partner, work
7. How has participating in the BASE study impacted your substance use disorder?

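### The sub-study interview guide has no question on how BASE participation affected mental health or access to support systems, though the secondary objective names both

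*Combined protocol and SAP*

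**What the plan says.** Addendum E sets out what the interviews are meant to deliver.

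- **Secondary objective** (Addendum E, Objectives): "Secondary: Determine BASE participant perspectives on how study participation impacted their on-going substance use, mental health, and access to necessary support systems". That is three domains.
- **Hypothesis** (Addendum E, Hypothesis): "BASE study participation positively impacted the participant's treatment adherence, motivations for engagement in care for HIV, substance use disorders, and mental health". It names mental health and does not name support systems.
- **Overview** (Addendum E, Study Design): besides treatment adherence and motivations for engagement in care, the effect of participation is to be examined for "on-going substance use, mental health, stigma, and access to the necessary support systems". That makes six domains.
- **Instrument** (Addendum E, Study Implementation): a semi-structured guide that "contains a listing of open-ended questions with subsequent sub-question probes to elicit participant experiences and perspectives regarding each core topic".
- **Number of contacts** (same section): "Only one in-depth interview will be conducted for each participant".

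The guide's introduction tells participants that the interest is in how participation affected "your motivations for engaging in medical care, your substance use, your mental health and your overall quality of life". The final themed section, on views and experiences of taking part, then asks about the effect of participation on several named matters. Two examples are "How has participating in the BASE study impacted your ability to take your medicine" (item 5) and "How has participating in the BASE study impacted your substance use disorder" (item 7).

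**The concern.** A qualitative study answers its objectives from what participants are asked to talk about. The guide largely works domain by domain, with a separate participation question for most of the domains in the overview, but mental health and access to support have none.

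If a domain is not raised with everyone, a theme on it comes from those participants who happened to bring it up. Silence from the rest cannot be read as no effect. With one interview per participant, the plan offers no later contact at which to ask. Sampling is planned at 20 to 25 participants or until thematic saturation, and saturation is hard to judge for a domain that is not put to each participant.

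For mental health there is a further problem. The hypothesis is directional (a positive effect), and the guide gives no systematic opportunity to report a neutral or negative one.

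**Working it through.** No sample size, power or error-rate figure is involved. The check is a reading of Appendix A, question by question, against the stated domains.

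**Step 1: count the questions.** Living with HIV 5, living with a substance use disorder 5, engagement in HIV care 5, views and experiences with participation 8, closing 1. Total 5 + 5 + 5 + 8 + 1 = 24.

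**Step 2: map the six overview domains to questions that ask about the effect of participation.** Item numbers refer to the views and experiences section.

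| Domain | Named in secondary objective | Named in hypothesis | Participation-linked question |
|---|---|---|---|
| Treatment adherence | no (primary) | yes | item 5 |
| Engagement in HIV care | no (primary) | yes | item 4 |
| Stigma | no | no | item 6 |
| Substance use | yes | yes | item 7 |
| Mental health | yes | yes | none |
| Access to support systems | yes | no | none |

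Four of the six overview domains have a matching question and two do not. Of the three domains in the secondary objective, one has a matching question and two do not. Of the four in the hypothesis, three do and one (mental health) does not.

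**Step 3: look for the two missing domains elsewhere in the guide.**

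- *Mental health.* The participant's own mental health is named once, in the introduction, which is a statement and not a question. The only other mention is in a probe under engagement in care (item 5, probe c), where it is a type of healthcare provider. Questions on the participant's own mental health by name: 0 of 24.
- *Support systems.* Two questions ask about them: item 2 under living with HIV and item 2 under living with a substance use disorder. Both cover initial and current support, with a probe listing sources such as family and support groups. Neither mentions BASE or asks whether access changed through taking part. Questions on support: 2 of 24. Questions on the effect of participation on access to support: 0 of 24.

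**Step 4: look for indirect routes.** Item 8 of the views section asks how participation helped or did not help with coping with HIV or substance use. It is linked to participation and borders on both domains, but names neither. The closing question invites anything not yet covered. These can produce relevant material, but they do not put either domain to every participant.

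**Step 5: check whether main-trial data fill the gap.** The SF-12 gives a mental score and is scheduled at baseline, week 24 and week 48. It measures health status. It does not record participants' views on what participation did, and Addendum E does not refer to it.

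**The case against.** The strongest reply is that this is a semi-structured, open-ended guide used by a trained qualitative interviewer for 1 to 2 hours, not a closed questionnaire. The introduction tells every participant that the effect on mental health is of interest. Item 8 asks about coping in relation to BASE. Item 3 asks whether the experience was positive or negative, and why. Probes under items 4 and 5 ask what helped or hindered during the study, and the closing question is open. The two support-system questions are also asked near week 48 (42 to 60 weeks), so current support is described after most of participation. On this view, requiring a named question for every domain is a matter of taste.

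Much of this stands, and it rules out three stronger readings that a reader might infer:

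- *That the guide asks nothing about support systems.* It asks about them twice. What is missing is the link to participation.
- *That the hypothesis also covers access to support.* It does not; only the secondary objective and the overview do.
- *That the two domains cannot be answered, or are unmeasured.* The indirect routes make that too strong.

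Nor does it count against the plan that the four interview topics listed under Study Implementation omit both domains. Those topics correspond to the guide's themed sections. They do not name adherence or stigma either, and both of those are asked about.

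What does not stand is the suggestion that nothing is missing. The guide is the stated means of eliciting perspectives, and it gives named participation questions to the other four domains. An interviewer who follows it as written would complete the interview without asking about the effect of participation on mental health or on access to support.

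**Conclusion.** The point holds in a limited form. Appendix A has no question or probe on how BASE participation affected the participant's own mental health, and its two support-system questions are not tied to participation. Two of the three domains in the secondary objective, and one of the four in the hypothesis, are therefore not directly or systematically elicited.

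This rests on reading the guide as written and assumes that interviewers add no standard probes beyond it. If they do, the gap is smaller, but the plan does not say so.

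The consequence is confined to the sub-study's secondary objective and the mental-health part of its hypothesis. The primary objective, on engagement and adherence, is covered by items 4 and 5 of the views section. No BASE trial endpoint, estimate or safety assessment depends on this guide. Priority is low, though the repair is cheap before the interviews and, with a single interview each, hard to make afterwards.

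**What to change.** Add two questions to the section of Appendix A on views and experiences with study participation: one on how taking part affected the participant's mental health, and one on how it affected access to support systems. Model both on item 7, with its probe asking whether things are better or worse than before the study, and why, so that neutral and negative answers are invited as well.

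The cost is a slightly longer interview within the planned 1 to 2 hours, and a minor amendment to Appendix A.

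The documents do not show whether interviewing has finished. If it has, narrow the secondary objective to what was asked, by removing or qualifying both domains, and narrow the hypothesis for mental health only. The report should state that material on these domains came from indirect questions, and that absence of mention is not evidence of no effect.

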Appendix A

Interview Question Guide: BASE Participants

PID: _____ Date: _____

Introduction:

Thank you for the opportunity to speak with me today. Please note that this conversation is confidential. We are interested in hearing your opinions and experiences regarding how your participation in the BASE study impacted your motivations for engaging in medical care, your substance use, your mental health and your overall quality of life. May I start by asking you about your experience living with HIV...

Living with HIV

1. What has your experience been like living with HIV?
 - a. Probe: When were you first diagnosed?
 - b. Probe: What experiences did you have coping with your HIV diagnosis?
2. What support systems did you initially have or currently have for coping with your HIV diagnosis?
 - a. Probe: friends, family, partner, support groups, etc
3. What were you initially told about HIV treatment?
 - a. Probe: What feelings did you have regarding the need for life-long treatment?
 - b. Probe: What feelings did you have knowing there was no cure for HIV infection?
4. What experiences have you had with stigma or discrimination because you are living with HIV?
 - a. Probe: Friends, family, partner, work
5. What is the hardest part of living with HIV?
 - a. Probe: Taking life-long medicine, coming to medical visits, dealing with stigma, worry of health, cost of care, etc.

Living with a substance use disorder

1. What has your experience been like living with a substance use disorder?
 - a. Probe: When did you first use an illicit drug and how has your substance use impacted your well-being?
 - b. Probe: What experiences did you have coping with your substance use?
2. What support systems did you initially or currently have for coping with your substance use disorder?
 - a. Probe: friends, family, partner, support groups, etc
3. In what ways has your substance use disorder affected your life?

- a. Probe: Medically, relationships, financial, etc.
4. What experiences have you had with stigma or discrimination because you have a substance use disorder?
 - a. Probe: Friends, family, partner, work
5. What are your experiences with receiving help for your substance use disorder?
 - a. Probe: Describe your experiences with trying to stop or reduce your substance use.
 - b. Probe: How many times have you tried to stop or reduce your substance use?
 - c. Probe: What have been the challenges with stopping or reducing your substance use?

Engagement in HIV care

1. What does being engaged in HIV care mean to you?
 - a. Probe: Would you describe your engagement in HIV care prior as good or bad? Why?
2. Tell us your experiences with coming to clinic appointments.
 - a. Probe: What barriers have kept you from coming to your appointments?
3. What are your views on what has kept you from coming to your clinic appointments?
 - a. Probe: Medication non-adherence, substance use, homelessness, etc
4. What interventions have helped you to come to your clinic appointments?
 - a. Probe: acute sickness, concern for your health, transportation assistance, gift cards, etc.
5. What experiences have you had with stigma or discrimination when coming to an HIV clinic appointment?
 - a. Probe: What are your feelings about the impact of HIV control (U=U) on stigma related to HIV infection or substance use disorders?
 - b. Probe: What have been your experiences during interactions with medical service providers?
 - c. Probe: Would you describe your experiences with various types of healthcare providers (medical [both HIV providers and non-HIV providers], mental health, etc) as different? Why?

Views and experiences with study participation

1. How did you hear about the BASE study?
 - a. Probe: What motivated you to enroll?
 - b. Probe: What interested you most about the study?
2. What concerns did you have about participating in the BASE study?
 - a. Probe: Privacy, stigma, legal concerns
3. Tell us about your experiences with BASE study participation.
 - a. Probe: Would you describe your experience as positive or negative? Why?

4. How has participating in the BASE study impacted your ability to come to your clinic appointments?
 - a. Probe: What are your feelings of your medical care during participation of the BASE study?
 - b. Probe: What factors have increased or decreased your ability to come to your clinic appointments during the course of the BASE study?
5. How has participating in the BASE study impacted your ability to take your medicine?
 - a. Probe: What factors have increased or decreased your ability to adhere to prescribed medications during the course of the BASE study?
6. What experiences have you had with stigma or discrimination because you participated in the BASE study?
 - a. Probe: Medical providers, friends, family, partner, work
7. How has participating in the BASE study impacted your substance use disorder?
 - a. Probe: Compared to before study participation, would you describe your substance use better or worse? Why?
8. In what ways has your participation in BASE helped you cope or not cope with your HIV diagnosis or substance use disorder?

Closing

1. Is there anything else that you feel is important for us to know that we haven't already asked about?
